6.9.2 Prohibited Medications and Non-Drug Therapies

Treatment with the following concomitant medication is prohibited:

- Use of topical treatments for AA within 2 weeks before the Baseline (Day 1) visit and until completion of the follow-up (including the extended follow-up) period, such as corticosteroids, calcineurin inhibitors, JAK inhibitors (e.g., ruxolitinib), antimicrobials, anthralin, DPCP, squaric acid, minoxidil or any other medication which, in the opinion of the investigator, may affect hair regrowth;

Note: Topical treatments are permitted outside of the scalp, eyebrows and eyelashes.

- Use of non-biologic systemic (oral or injectable) agents including conventional immunosuppressants or immunomodulators (e.g., corticosteroids, methotrexate, MMF, cyclosporine A, azathioprine, hydroxychloroquine, sulfasalazine and other approved drugs with potential immunosuppressive effects, within 4 weeks or 5 half-lives, whichever is longer, prior to the Baseline (Day 1) visit and until completion of the follow-up (including the extended follow-up) period;
- Use of oral JAK inhibitors within 8 weeks prior to the Baseline (Day 1) visit and until completion of the follow-up (including the extended follow-up) period;

- Use of oral or injectable agents (minoxidil, apremilast, finasteride, HMG-CoA reductase inhibitors [statins], herbal medicines) for the treatment of AA within 4 weeks prior to the Baseline (Day 1) visit and until completion of the follow-up (including the extended follow-up) period;

*Note that the listed medications are permitted if they are not indicated for the treatment of AA **AND** have been used at a stable dose until the completion of the study. These medications are prohibited if they are indicated for the treatment of AA **OR** if they have been newly initiated or had their dose modified during the study.*

- Use of any biologic therapy (e.g., mAbs against IL-17, IL-4, and IL-13 or other investigational products) or platelet-rich plasma within 3 months or 5 half-lives, whichever is longer, prior to the Baseline (Day 1) visit and until completion of the follow-up (including the extended follow-up) period;
- Use of phototherapy for the treatment of AA within 4 weeks before the Baseline (Day 1) visit and until completion of the follow-up (including the extended follow-up) period, such as UVA or UVB, or any other type of light therapy that, in the opinion of the investigator, may affect hair regrowth.
- Receipt of a live vaccine, including live attenuated, within 2 months before the Baseline (Day 1) visit and until 3 months after the last administration.
- Other medications or non-drug therapies, in the opinion of the investigator, that could affect AA from screening to study completion.

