2.3 Alopecia Areata

Alopecia areata (AA) is a chronic relapsing and remitting autoimmune disease characterized by nonscarring hair loss involving the scalp, face, and/or body. It can affect children and adults of all ages, races and genders but more commonly in females and non-whites especially Asians ([Mostaghimi et al 2023; Harries et al 2022](#)). Approximately 2% of the general population can be affected by AA during their lifetime ([Pratt et al 2017](#)). The point prevalence rates of AA based on recent studies using electronic healthcare records were approximately 0.22% in the United States (US) ([Mostaghimi et al 2023](#)) and 0.58% in the United Kingdom ([Harries et al 2022](#)).

AA typically presents with well-demarcated patches of hair loss, most commonly on the scalp, but it may also involve the beard, eyebrows, eyelashes, and nails. In severe cases, AA involves the full scalp (alopecia totalis [AT]) or even full body (alopecia universalis [AU]). AA involving 50% or greater scalp hair loss, including AT and AU, is considered an advanced form ([King, Senna et al 2022; King, Mesinkovska et al 2022](#)). AA is associated with other inflammatory and autoimmune diseases including atopic diseases (e.g., atopic dermatitis [AD] and allergic rhinitis), autoimmune diseases (e.g., thyroiditis, lupus erythematosus), metabolic syndrome, and psychiatric disorders ([Lee et al 2019](#)). AA significantly impacts patients' daily life and often leads to profound psychological distress, social isolation, anxiety, and depression ([Pratt et al 2017; Mesinkovska et al 2020](#)).

The exact pathogenesis of AA is not fully understood. It involves a complex interplay between genetics, environmental factors, and adaptive immune response to unknown antigens. It is thought that the collapse of follicular immune privilege leads to activation and infiltration of immune cells, primarily CD4⁺ and CD8⁺ T cells, and also natural killer cells, mast cells, and dendritic cells, which swarm and attack the hair bulbs (Bertolini et al 2020; Olayinka et al 2021). Hair follicle cells in turn release more cytokines and chemokines that further recruit T cells and other immune cells forming positive feedback loops that shorten and distort the hair cycle. Activation of T cell subsets including T-helper (Th) type 1 (Th1) and Th2 cells in AA patients is associated with disease severity or chronicity (Czarnowicki et al 2018; Glickman, Dubin, Renert-Yuval et al 2021).

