7.3.5 Investigator's Global Assessment of Fingernails

At the scheduled clinical visits, the investigator will rate the severity of fingernail changes as it looks on the day of study visit on a 5-point scale ranging from 0 = “no” to 4 = “very severe”.

The investigator's global assessment of fingernails (IGA-FN) will be performed by the investigator. Further details on IGA-FN will be provided in the Study Reference Manual.

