#### Investigator’s Global Assessment (Eyebrows, Eyelashes, and Fingernails)

At the scheduled clinical visits, the investigator will rate the severity of eyebrow hair loss (IGA-EB), eyelashes hair loss (IGA-EL), and fingernail changes (IGA-FN) as it looks on the day of study visit on a 5-point scale ranging from 0 = “no” to 4 = “very severe”.

The investigator’s global assessment will be performed by the investigator.

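### The topical-treatment note leaves fingernails as the one scored site it does not protect, and whether nail-applied topicals trigger the SAP's prohibited-medication handling is left to investigator judgement

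*Protocol*

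**What the plan says.** Protocol 6.9.2 opens its list of prohibited treatments with this item: "Use of topical treatments for AA within 2 weeks before the Baseline (Day 1) visit and until completion of the follow-up", with the extended follow-up included. For topicals not listed by name, the test is whether they are "any other medication which, in the opinion of the investigator, may affect hair regrowth". Directly below stands the exception: "Topical treatments are permitted outside of the scalp, eyebrows and eyelashes". Protocol 5.2 (criterion 12) and SAP 4.3 repeat it, so it governs entry, conduct and the SAP's own definition of prohibited medication.

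The same list ends, in both Protocol 6.9.2 and SAP 4.3, with a catch-all for other drugs or non-drug therapies that the investigator believes could affect AA.

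Nails belong to the disease under study. Protocol 2.3 says of AA that "it may also involve the beard, eyebrows, eyelashes, and nails". Nails are also scored for efficacy. For IGA-FN, Protocol 7.3.5 provides that "the investigator will rate the severity of fingernail changes as it looks on the day of study visit on a 5-point scale", and participants rate their fingernails on PGIS-FN and PGIC-FN (Protocol 7.3.6 and 7.3.7). SAP 4.5.2 describes all three among the exploratory efficacy variables. The schedule of assessments limits the site-specific scales to participants with AA at those sites.

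**The concern.** The note protects three of the four sites on which efficacy is scored. As worded, a participant with nail disease could begin a topical on the nails after Baseline without leaving the permitted range. If such a topical improves the nails, the improvement falls within the same scores that are meant to describe the effect of IMG-007. The study is open label with two IMG-007 dose cohorts and no control arm, so no comparison would separate the two effects. What is at stake is the reading of three exploratory nail outcomes in the subset of participants with nail involvement.

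**Working it through.** The plan states no figure on this point, so there is none to reproduce. The check is a comparison of text, followed by an illustration of scale.

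**1. Sites scored against sites protected**

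| Site | Site-specific efficacy scales | Named in the topical note |
|---|---|---|
| Scalp | SALT, IATS, PGIS-S, PGIC-S | Yes |
| Eyebrows | IGA-EB, PGIS-EB, PGIC-EB | Yes |
| Eyelashes | IGA-EL, PGIS-EL, PGIC-EL | Yes |
| Fingernails | IGA-FN, PGIS-FN, PGIC-FN | No |

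**2. Conditions on the exception.** The note in Protocol 6.9.2 on oral or injectable agents requires both that the drug is not given for AA and that its dose is stable. The topical note carries neither condition. The test for unlisted topicals is an effect on hair regrowth, which does not reach nails.

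**3. Does another clause prohibit a nail topical?** Possibly. The catch-all could be applied to it. Protocol 6.9 requires each concomitant drug to be checked against the prohibited list, and 6.9.1 refers doubtful cases to the medical monitor. None of these clauses names nails or withdraws the permission in the note. The classification is therefore a judgement, and sites may differ.

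**4. What the SAP does in each case.** SAP 5.7.2.2 counts a participant as a non-responder on binary endpoints after prohibited medication starts. SAP 5.10.1 sets most pharmacodynamic data to missing after prohibited medication and describes this as like the handling of the secondary efficacy assessment. SAP 5.7.3 applies the intercurrent-event handling of 5.7.1 and 5.7.2.2 to the other exploratory variables and plans no sensitivity analysis for them. So:
- nail topical classed as prohibited: the handling applies;
- nail topical classed as permitted: neither visible rule is triggered, and later nail scores enter as observed.

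The rule for continuous endpoints does not appear in the public text of SAP 5.7.1. It is inferred here from 5.10.1.

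**5. Illustration of scale.** The documents give about 30 participants (6 + 24). They do not give the share with nail disease, so 10%, 20% and 40% are assumptions. With n = 30 × share, one participant moves a proportion by 1/n:
- 10%: n = 30 × 0.10 = 3; 1/3 = 33.3 points
- 20%: n = 30 × 0.20 = 6; 1/6 = 16.7 points
- 40%: n = 30 × 0.40 = 12; 1/12 = 8.3 points

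This applies only if a nail responder proportion is reported. None is visible in Protocol Table 3 or SAP 4.5.2. If the nail scales are summarised as means, the shift depends on the size of the individual change, which cannot be derived from the documents.

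**The case against.** A reader might infer that the SAP's prohibited-medication handling can never apply to a nail topical, or that nail improvement from topicals will be credited to IMG-007. The documents support neither.

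- **Catch-all.** An investigator may class a nail topical used for AA as prohibited, since nails are a recognised site of the disease, and the SAP handling would then follow. This stands against the word never. It does not settle the matter, because an explicit permission and a discretionary prohibition then point in different directions.
- **Meaning of the note.** It may be meant only for topicals given for other conditions elsewhere on the body; the protocol mentions comorbid atopic dermatitis. On that reading a nail topical for AA stays prohibited. The note does not say this, however, and it qualifies an item that concerns topicals for AA. Both readings remain open.
- **Treatment policy.** The protocol synopsis names a treatment-policy estimand for all efficacy analyses, under which later scores would be kept in any case. The SAP departs from this for prohibited medication on binary endpoints, so the classification still matters.
- **No evidence of use or effect.** The documents give no expected frequency of nail topicals, and Protocol 2.3 describes topical treatment of AA as having limited efficacy. A topical in stable use at Baseline is also already reflected in the baseline score. This stands: the bias is possible, not shown, and arises mainly when use starts or changes after Baseline.
- **Traceability.** The listings in SAP 5.3 include indication, route and start date, so use is partly identifiable. Application site is not among the fields named there. The case report form is not available, so it may already be captured.

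**Conclusion.** The mismatch stands as a minor point. Fingernails are scored but not covered by the note, and whether a nail topical triggers the SAP handling rests on investigator judgement. If it is treated as permitted, IGA-FN, PGIS-FN and PGIC-FN scores recorded afterwards would be analysed as observed, on the visible rules, with no control arm and no planned sensitivity analysis.

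The reach is limited to exploratory, descriptive outcomes in participants with nail disease. The primary endpoint (treatment-emergent adverse events) and the secondary endpoint (percentage change in SALT at Week 24) are untouched, since the scalp is a protected site.

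The size cannot be computed from the documents. The range of about 8 to 33 points rests on three assumptions: that 10-40% of 30 participants have nail disease, that a nail responder proportion is reported, and that one participant improves because of a nail topical.

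**What to change.** - **Reconcile the text.** Bring the note in Protocol 5.2 (criterion 12), Protocol 6.9.2 and SAP 4.3 into agreement with the catch-all and the fingernail assessments. Which clinical rule should apply is for the sponsor to decide; the passages need to give one answer.
- **SAP.** Whatever that answer is, name topical therapy applied to the nails and started or changed after Baseline as an intercurrent event for IGA-FN, PGIS-FN and PGIC-FN. Handle it as prohibited medication is handled for the other sites.
- **Data.** Identify the application site in the concomitant medication record, if it is not captured already.

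The cost is a sentence or two of SAP wording, aligned text in three places and possibly one data field. The downside is that a few nail observations would be set to missing or counted as non-response, in a subset that is already small.

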6.10 Early Withdrawal from Study

6.10.1 Discontinuation of Study Treatment

6.10.1.1 Permanent Discontinuation of Study Treatment

[REDACTED]

[REDACTED]

[REDACTED]

[REDACTED]

[REDACTED]

[REDACTED]

[REDACTED]

- [REDACTED]
- [REDACTED]
- [REDACTED]
- [REDACTED]
- [REDACTED]
- [REDACTED]
- [REDACTED]

- Participant receives an investigational drug (other than IMG-007)
- Lack of efficacy/activity of the study treatment, defined as inadequate improvement in disease activity based on investigator's clinical judgment
- Physician decision
- Study is stopped by the Sponsor or health authority.

Note that discontinuation of study treatment does not represent withdrawal from the study. If study treatment is discontinued early, efforts should be made to perform the remaining study visits through EOS.

6.10.1.2 Temporary Discontinuation of Study Treatment

A participant who meets either of the below criteria will have the study treatment temporarily discontinued until the laboratory abnormality recovers and/or event resolution.

- White blood cell count $< 3,000/\text{mm}^3$ ($< 3.0 \times 10^9/\text{L}$) confirmed upon repeat testing.
- Any infection (viral, bacterial, and fungal) requiring parenteral antimicrobial therapy or requiring oral medication(s) for longer than 2 weeks.

Note that the decision to restart the study treatment following any laboratory abnormality or infection described above will be made in consultation with the medical monitor.

6.10.2 Participant Withdrawal from the Study

In accordance with the Declaration of Helsinki and other applicable regulations, a participant has the right to withdraw from the study at any time at his/her own request or may be withdrawn at the discretion of the investigator for safety, compliance or administrative reasons.

A participant might withdraw from the study for any of the reasons below:

- Voluntary withdrawal of consent or study participation, at any time
- A participant's failure to comply with the protocol requirements or study-related procedures
- An intercurrent or safety event which, in the opinion of the investigator, requires the withdrawal of the participant
- Lost to follow-up
- Death

If a participant cannot or will not continue in the trial, the participant should complete the EOS visit procedures instead of the planned visit. All information, including the reason for early withdrawal, will be recorded in the participant's study records and in the case report form (CRF).

For participants who are lost to follow-up or withdraw their consent to participate in the study, the procedures of withdrawal from the study will no longer apply.

6.10.3 Lost to Follow-Up

A participant will be considered lost to follow-up if he or she repeatedly fails to return for scheduled visits and is unable to be contacted by the study site.

The following actions must be taken if a participant fails to return to the clinic for a required study visit:

- The site must attempt to contact the participant and reschedule the missed visit as soon as possible, counsel the participant on the importance of maintaining the assigned visit schedule and ascertain whether the participant wishes to and/or should continue in the study.
- Before a participant is deemed lost to follow-up, the investigator or designee must make every effort to regain contact with the participant (where possible, three telephone calls, and if necessary, a certified letter to the participant's last known mailing address or local equivalent methods). These contact attempts should be documented in the participant's medical record.
- Should the participant continue to be unreachable, the participant will be considered to have withdrawn from the study.

6.11 Premature Termination or Temporary Suspension of the Study

The Sponsor reserves the right to terminate the study prematurely at any time for any reason at the sole discretion of the Sponsor. Any premature discontinuation will be appropriately documented according to local requirements (e.g., institutional review board [IRB]/ethics committee [EC], regulatory authorities, etc.).

Reasons for early closure of a study site by the Sponsor or investigator may include but are not limited to:

- For study termination:
 - Discontinuation of further study intervention development
- For site termination:
 - Failure of the investigator to comply with the protocol, the requirements of the IRB/independent ethics committee (IEC) or local health authorities, the Sponsor's procedures, or GCP guidelines
 - Inadequate or no recruitment (evaluated after a reasonable amount of time) of subjects by the investigator

If the study is prematurely terminated or suspended, the Sponsor shall promptly inform the investigators, the IEC/IRBs, the regulatory authorities, and any CRO(s) used in the study of the reason for termination or suspension, as specified by the applicable regulatory requirements. The investigator shall promptly inform the participant and should assure appropriate participant therapy and/or follow-up.

The study may resume once concerns about safety, protocol compliance, and data quality are addressed, and satisfy the Sponsor, IRB/ IEC and/or regulatory authorities.

6.12 Study Stopping Rules

- [REDACTED]
- [REDACTED]
- [REDACTED]
- [REDACTED]
- [REDACTED]

[REDACTED]

[REDACTED]

7 STUDY PROCEDURES AND ASSESSMENT

7.1 Study Procedures

7.1.1 Informed Consent Procedure

Informed consent must be obtained before a participant enters the trial and before any protocol-directed procedures are performed. The requirements of informed consent are described in [Section 12.3](#).

7.1.2 Screening Period

Screening evaluations will be performed for all participants to determine study eligibility. These evaluations must be completed within 35 days prior to the first dose of study treatment. A screen failure is defined as a participant who has given informed consent and failed to meet the inclusion and or/exclusion criteria. Participants who fail to meet inclusion criteria or who meet exclusion criteria can be rescreened once per investigator discretion. Each participant must be re-consented prior to each screening attempt.

If needed, eligible participants who have completed screening procedures but are not enrolled due to scheduling-related delays, site logistics, or Sponsor-imposed delays (e.g., due to protocol amendments or other), the screening window may be extended for up to three business days.

Safety laboratory analysis will be performed centrally. Screening laboratory values must demonstrate subject eligibility, but may be repeated within the screening window, if necessary.

Screening procedures and assessments performed at screening is specified in the SoA (see [Table 1](#)).

7.1.3 Treatment Period

Eligibility must be confirmed at the Baseline (Day 1) visit before any other assessment/procedure is performed.

Participants will receive three IV infusions of IMG-007 [REDACTED] or [REDACTED] administered 2 weeks apart at the Baseline (Day 1), Week 2 (Day 15), and Week 4 (Day 29) visits. Participants will complete additional visits at Week 1 (Day 8), Week 6 (Day 43), Week 8 (Day 57), Week 12 (Day 85) and Week 16 (Day 113)/EOT.

Study procedures and their timing are summarized in the SoA ([Table 1](#)). Assessments/procedures at a clinic visit should be performed in the following order:

1. Participant-reported outcomes

2. Investigator assessments (performed only by adequately trained investigators or sub-investigators; the same investigator or sub-investigator should perform all the evaluations for a given participant throughout the entire study period where feasible to minimize inter-assessor variability)
3. Safety and laboratory assessments
4. Administration of study treatment at the Baseline (Day 1), Week 2 (Day 15), and Week 4 (Day 29) visits.

Adherence to the study design requirements, including those specified in the SoA ([Table 1](#)), is essential and required for study conduct.

Repeat or unscheduled samples may be taken for safety reasons at the discretion of the investigator or for technical issues with the samples.

In the event of a significant study-continuity issue (e.g., caused by a pandemic), alternative strategies for the visits, assessments and monitoring may be implemented by the Sponsor or the investigator, as per local health authority/ethics requirements.

The investigator may discontinue a participant's study treatment at any time during the study when the participant meets the study treatment discontinuation criteria described in [Section 6.10.1](#).

In addition, every effort should be made to perform all procedures scheduled for the EOT visit. Study staff will record the AE(s) as reported by the participant or observed by the investigator. They will record vital signs, results of the 12-lead electrocardiogram (ECG), or other assessments, including the information to be recorded. Study staff will collect blood/urine for the appropriate laboratory tests. They will also record the participant's adherence to protocol procedures.

7.1.4 Follow-up Period

The participant must return to the study center for follow-up visits and complete the procedures for safety, PK, PD, immunogenicity, and efficacy evaluations. The details for follow-up procedures are outlined in the SoA ([Table 1](#)).

7.1.5 End of Study

The EOS visit will be at Week 24 (Day 169).

A participant may discontinue his or her participation without giving a reason at any time during the study. Should a participant's participation be discontinued, the primary criterion for termination must be recorded by the investigator.

